### 9.4 STATISTICAL ANALYSES

Below are the pre-specific outcome measures:

Primary Outcome Measure:

1. Variability in Peak Inspiratory Flow (PIF) Measured via Digihaler Device (Time Frame: Three months)
  - b. PIF is the maximal flow occurring during an inhalation effort, expressed in Liters/minute. Mean, standard deviation and coefficient of variation (calculated by dividing standard deviation of PIF by the mean of the PIF) of daily PIF measurement collected over three months will be calculated. PIF will be measured using the Digihaler device.

Secondary Outcome Measures:

1. Correlation of Self-Reported Inhaler Use with Actual Inhaler Use (Time Frame: 3 months)

- a. Correlation between self-reported inhaler use and actual inhaler use over three months will be calculated with Spearman rank-order correlation coefficient. Self-reported inhaler use will be determined with an investigator-developed single question categorizing average use over the last four weeks with five groups (not at all, once a week or less, two or three times a week, one or two times a day, three or more times a day). Actual inhaler use will be directly measured via Digihaler device and categorized into one of the five groups described above.
2. Variability in Inhalation Volume Measured via Digihaler (Time Frame: Three months)
  - a. Inhalation volume is the volume of air inspired during an inhalation effort, expressed in Liters. The mean, standard deviation and coefficient of variation (calculated by dividing standard deviation of inhalation volume by the mean of the inhalation volume) of daily inhalation volume measurements collected daily over three months will be calculated. Inhalation volume will be measured using the Digihaler device.

The primary analysis will be descriptive, with analytical plans as defined above for each primary and secondary outcome.

The primary analysis will be descriptive, with analytical plans as defined above for each primary and secondary outcome.

Additional exploratory analysis will include linear regression (continuous) or negative binomial regression (count) of the clinical and demographic factors associated with inhaler from primary and secondary outcomes; descriptive statistics (mean, median, variance estimate and 95% confidence intervals) of number of inhalation events, correlation of inhaler metrics (PIF, inhalation volume, number of inhalation events) with CAT score, correlation of inhaler metrics (PIF, inhalation volume, number of inhalation events) with daily self-assessment asking “How are you feeling?” with responses provided on a Leikert scale, correlation of inhaler metrics (PIF, inhalation volume, number of inhalation events) with responses to metric algorithm-triggered DAQ; change in inhaler metrics (during the 7 days after and/or leading into hospitalized AECOPD or home treatment of a moderate AECOPD defined by a prescription for steroids and/or antibiotics); descriptive statistics (proportion, 95% CI) of COPD-associated hospitalizations and emergency room visits as well as SABA utilization; and patient satisfaction will be assessed with a post-study survey. The Leikert scale will be modeled using an ordinal scale with lower number signifying worse daily overall feeling. The DAQ will be comprised of yes/no responses to a set of questions (categorized as No=0; Yes=1) with higher score calculated in the analysis indicating worse symptoms. In exploratory analyses, individual DAQ domains and cumulative score will be evaluated as outcomes. Because the DAQ also includes the Leikert scale, on days where both the DAQ Leikert and daily Leikert are completed, the DAQ Leikert will be used for analysis.

---

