## 2.2 BACKGROUND

Chronic obstructive pulmonary disease (COPD) is the 4th leading cause of death in the United States. It is characterized by fluctuating respiratory symptoms punctuated by transient acute worsening termed acute exacerbations of COPD (AECOPD). The optimal management of COPD requires accurate assessment of respiratory symptom burden, prevention, timely identification and early intervention on AECOPD ([www.GOLD.org](http://www.GOLD.org)). A key component of symptom management is the use of inhaled short-acting beta-agonists (SABA). Per treatment strategies, all individuals with spirometry-confirmed COPD (regardless of severity) should be prescribed SABA therapy. Accurate assessment of SABA use is essential in COPD, as it not only informs overall symptom control but also may also herald onset of an AECOPD event. Unfortunately, several studies have demonstrated that physicians are ineffective at accurately assessing SABA usage as a marker of disease control, as patients often misreport their actual use. Moreover, there are no technologies that could serve to automatically alert a patient or provider about abrupt increases in SABA use or decreases in inspiratory flow rate, which may both identify an impending AECOPD. Closing these assessment gaps through real-time electronic capture of SABA use has the potential to improve the assessment and care of COPD patients in the chronic setting and during acute decompensation.

There are several factors that can impact successful SABA administration. These include inhalation technique, duration, and inspiratory effort. Dry-powder inhalers (DPIs) are breath-actuated and tend to be easier for patients to use than metered dose inhaler or soft mist inhalers. However, there is emerging evidence that delivery from DPI may be suboptimal in some patients and settings. It has recently been shown that COPD patients can exhibit suboptimal peak inspiratory flow (PIF) in the stable outpatient setting (Ghosh, Sulaiman) and during hospital exacerbations (Loh, Sharma). Although published evidence regarding suboptimal delivery from DPIs in the COPD population is emerging, substantial knowledge gaps exist including the day to day variation in PIF in ambulatory COPD patients when clinically stable and during periods leading up to and recovery from AECOPD.

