## 3 OBJECTIVES

### Primary Objective:

- To determine the variation in ProAir Digihaler metrics (PIF, inhalation volume, number of inhalation events) amongst COPD patients in the ambulatory setting.

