**Secondary Objectives.**

- To determine the correlation of self-reported SABA use with actual SABA use collected by the ProAir Digihaler.
- To determine the correlation of inhaler metrics (PIF, inhalation volume, number of inhalation events) with monthly CAT score domains.
- To determine the correlation of inhaler metrics (PIF, inhalation volume, number of inhalation events) with the daily self-assessment asking “How are you feeling?” with responses provided on a Leikert scale.

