## 9 STATISTICAL CONSIDERATIONS

### 9.1 HYPOTHESIS

We hypothesize that inhaler metrics (PIF, inhalation volume, rescue inhaler use) will vary among COPD populations. We also hypothesize that increased albuterol use will positively correlate with worse daily Leikert scores, declining PIF, lower inhalation volume and higher CAT scores. We hypothesize that self-reported albuterol use will be lower than actual albuterol use captured by the DAQ app. We hypothesize that increased albuterol use will positively correlate with more symptomatic DAQ responses. The proposed study is designed to yield an initial exploration of the metrics captures by the Digihaler in a COPD population.

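### The plan hypothesises that self-reported albuterol use is lower than device-measured use, but its only comparison is a Spearman correlation, which cannot show direction; the device grouping rule is also incomplete

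*Combined protocol and SAP*

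**What the plan says.** The secondary objective (Section 3, repeated in the synopsis) is "To determine the correlation of self-reported SABA use with actual SABA use collected by the ProAir Digihaler". The matching outcome in Section 9.4, also in the synopsis, is analysed as follows: "Correlation between self-reported inhaler use and actual inhaler use over three months will be calculated with Spearman rank-order correlation coefficient".

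Self-report comes from a single question on average use over the last four weeks, with five answers. The first is no use at all; the other four are "once a week or less, two or three times a week, one or two times a day, three or more times a day". For the device side, Section 9.4 says: "Actual inhaler use will be directly measured via Digihaler device and categorized into one of the five groups described above". It gives no numerical cut-points, rounding rule or counting unit. Section 8.1 lists device usage only as a count.

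Section 9.1 states a directional hypothesis: "We hypothesize that self-reported albuterol use will be lower than actual albuterol use captured by the DAQ app". Section 2.2 motivates it with the statement that "patients often misreport their actual use".

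The exploratory part of Section 9.4 adds descriptive statistics of inhalation events and of "COPD-associated hospitalizations and emergency room visits as well as SABA utilization". It does not set either against self-report.

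**The concern.** The hypothesis is about level: is self-report below the device record? The planned statistic is about ordering: do participants who report more also use more? These are different questions, and only the second has an analysis. Followed as written, the plan would end with a correlation coefficient and nothing to say about under-reporting, although both measurements are in hand.

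The second issue is reproducibility. The five answers work as choices offered to a patient, who picks the nearest. A device produces a number, and many numbers fall between the labels. Two analysts applying the same text could assign the same participant to different groups. The unit adds to this: Section 6.1.2 describes two inhalations per administration, the device metric is inhalation events, and the labels speak of times. Once under-reporting is examined directly, either choice could create or hide it. Both therefore need to be settled before the data are seen.

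**Working it through.** The documents give no power, effect size or use distribution for this outcome, so there is no stated figure to reproduce. The target of 60 participants comes from Section 5.4. All distributions below are assumptions for illustration. The shift, symmetry and gap results do not depend on them.

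**1. What Spearman can see.** Spearman's rho is the Pearson correlation of the ranks. Subtracting one group from every self-report leaves all ranks unchanged, and rho(X, Y) = rho(Y, X). Take 60 participants, 15 in each of device groups 2 to 5.

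| Self-report | rho | Mean difference (self-report minus device, in groups) |
|---|---|---|
| All accurate | 1.00 | 0 |
| All one group too low | 1.00 | -1.00 |
| 20 one group too low (5 per device group), 8 one too high (3, 3 and 2 in groups 2 to 4) | 0.855 | (8 - 20)/60 = -0.20 |
| Third row with the two columns swapped | 0.855 | +0.20 |

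After the swap, device groups 1 to 5 hold 5, 12, 15, 16 and 12 participants, so the marginal distribution changes. The point is only that rho is identical while the direction reverses.

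A direct summary of the third row separates the two directions:
- under-reporting: 20/60 = 33% (Wilson 95% CI 23-46%)
- over-reporting: 8/60 = 13% (7-24%)
- exact two-sided sign test, 20 against 8: p = 0.036

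**2. Gaps in the device groups.** Convert each label to a 28-day total:
- none: 0
- once a week or less: 1-4
- two or three a week: 2 × 4 = 8 to 3 × 4 = 12
- one or two a day: 1 × 28 = 28 to 2 × 28 = 56
- three or more a day: 3 × 28 = 84 and above

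The totals left over are 5-7 (3 values), 13-27 (15) and 57-83 (27). That is 45 of the 84 possible totals from 0 to 83. A rounding convention does not settle this by itself. Rounding the daily average to the nearest whole number first places every total. Rounding the weekly average, for use below once a day, still leaves 14-25 unplaced.

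**3. Effect of the placing on rho.** Suppose k of 60 participants have totals in 13-27, all give the same neighbouring answer (group 3 or 4), and everyone else is accurate. If the rule puts the k participants in the group they chose, rho = 1.00. If it puts them in the other group, rho depends on where the remaining 60 - k lie:

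| k | Others spread as evenly as possible over groups 2-5 | Others split between groups 3 and 4 |
|---|---|---|
| 3 | 0.98 | 0.90 |
| 6 | 0.96 | 0.82 |
| 12 | 0.92 | 0.67 |

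The last column can be checked by hand. With only two groups occupied, rho = sqrt{n3·n4 / [(n3 + k)(n4 + k)]}, where n3 and n4 are the numbers of other participants in groups 3 and 4.
- k = 12: n3 = n4 = 24, so rho = 24/36 = 0.67
- k = 6: n3 = n4 = 27, so rho = 27/33 = 0.82
- k = 3: n3 = 28 and n4 = 29, so rho = sqrt(812/992) = 0.90

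The mean paired difference moves by k/60, which is 0.05, 0.10 or 0.20 group, in both columns.

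**4. Effect of the unit.** Take 60 accurate reporters, 10 at each of 1, 2 and 3 times a week and 1, 2 and 3 times a day, with exactly two inhalations per occasion. Their 28-day totals are 4, 8, 12, 28, 56 and 84 occasions, or 8, 16, 24, 56, 112 and 168 inhalations.
- Counting occasions, none appears to under-report.
- Counting inhalations with cut-points 0; 1-4; 5-27; 28-83; 84 or more, those at 1 a week and 2 a day move up a group: 20/60 = 33%.
- Counting inhalations with the boundary between groups 3 and 4 moved to 12/13, those at 2 and 3 a week move up as well: 40/60 = 67%.

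**The case against.** The strongest reply is that the outcome and objective are both worded as a correlation, and Spearman on ordered groups is a sound choice for that. This stands. A reader might infer that Spearman is the wrong analysis for secondary outcome 1; the documents do not support that reading. The mismatch is with the hypothesis in Section 9.1.

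A second reply is that this is a pilot: Section 9.1 calls it an initial exploration, Section 9.2 disclaims power, and Section 9.4 calls the analysis descriptive. That limits the weight of the point and argues against insisting on a formal test. It does not remove the point, because proportions with confidence intervals are themselves descriptive, and no sample size would let rho show direction.

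Third, it may be said that the cut-points matter only for an added comparison and hardly affect Spearman. That depends on the use distribution. The loss is small if participants are spread over groups 2 to 5, and large if they cluster around the boundary between groups 3 and 4. Neither a negligible effect nor a fixed upper bound can be claimed.

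Fourth, the full wording of the self-report question is not shown, and it may define a time. That is fair. A reader might infer that the patient's question is ambiguous, which the documents cannot establish. What is missing is the unit on the device side.

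**Conclusion.** The concern holds in a limited form. The hypothesis that self-report is lower than device use has no analysis that could support or refute it, because the one planned comparison is blind to a uniform shift and to direction. This follows from the definition of Spearman's rho and needs no assumed data.

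The five device groups, read literally, omit 28-day totals 5-7, 13-27 and 57-83, and the device-side unit is unstated. This follows from the labels alone. It would go too far to say the grouping is undefined: five ordered labels are given, and the first two meet without a gap.

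The sizes are conditional. The fall in rho (to 0.98, 0.96 or 0.92, or to 0.90, 0.82 or 0.67), and the 33% and 67% apparent under-reporting from the choice of unit, rest on assumed use distributions. The unit figures also assume exactly two inhalations per occasion.

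This should be fixed, but its reach is one descriptive secondary outcome and one stated hypothesis. The primary outcome and safety are unaffected.

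**What to change.** Keep the question and the Spearman coefficient. Add to the SAP:

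1. A cross-tabulation of self-report group against device group, with the proportions of participants under-reporting and over-reporting and their 95% CIs. Use one value per participant, for example month 1, which Section 9.3 already requires for inclusion in the analysis. If months are pooled, resample by participant. A paired sign or signed-rank test and a weighted kappa are optional.
2. Contiguous device cut-points fixed before the data are seen, for example 28-day totals 0; 1-4; 5-27; 28-83; 84 or more. As a sensitivity analysis, move the boundary between groups 3 and 4 to 12/13.
3. The device-side counting unit (inhalation or occasion of use), with the other unit as a sensitivity analysis.

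The cost is SAP wording and a little more analysis, with no new visits or data. Some limits remain. Placing near the boundary between groups 3 and 4 stays approximate, because someone between those answers had to choose one. Participants in the lowest device group cannot under-report, and those in the highest cannot over-report. Precision is modest: 30/60 under-reporting would give a 95% CI of 38-62%.

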### 5 STUDY POPULATION

#### 5.1 INCLUSION CRITERIA

- Age >40 years old
- History of cigarette smoking >=10 pack-years
- Established COPD defined as physician diagnosis along with spirometry confirmation (post-BD FEV1/FVC<0.70) within the last two years and an FEV1 ≤80% predicted
- Regular albuterol use (defined as at least one puff weekly for each of the last four weeks)
- Currently non-hospitalized
- Medical records confirmed history of two moderate AECOPD (defined as use of antibiotic or steroids to treat clinical event consistent with AECOPD) or one severe AECOPD (defined as ED/hospital visit) in prior 12 months
- Access to smartphone, tablet or computer and internet
- Willingness to switch current rescue inhaler/device to ProAir Digihaler

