## 6.1.2 DOSING AND ADMINISTRATION

ProAir Respclick will be dosed and administered in accordance with the package insert ([https://www.accessdata.fda.gov/drugsatfda\\_docs/label/2015/205636s000lbl.pdf](https://www.accessdata.fda.gov/drugsatfda_docs/label/2015/205636s000lbl.pdf)). Specifically, albuterol sulfate 117 mcg will be administered 2 inhalations repeated every 4 to 6 hours as needed.

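### Grouping the Digihaler count to match the questionnaire hides misreporting that stays at or above three uses a day; adding the ungrouped device rate recovers part of the lost detail at almost no cost (minor)

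*Combined protocol and SAP*

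**What the plan says.** Section 9.4 (Secondary Outcome Measure 1), repeated under Outcome Measures in the synopsis, uses a single question about average use over four weeks with five ordered answers. The list of answers closes with the two highest, and the rule for the device follows at once: "one or two times a day, three or more times a day). Actual inhaler use will be directly measured via Digihaler device and categorized" into the same five groups. The association "will be calculated with Spearman rank-order correlation coefficient".

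Section 6.1.2 gives the dosing as "2 inhalations repeated every 4 to 6 hours as needed". Section 5.1 sets the minimum use for entry: "Regular albuterol use (defined as at least one puff weekly for each of the last four weeks". Section 9.1 states the expected direction: "We hypothesize that self-reported albuterol use will be lower than actual albuterol use captured by the DAQ app". Section 2.2 gives the reason for looking: "patients often misreport their actual use".

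The device count is also kept ungrouped. Section 8.1 lists usage as a count, and the exploratory part of section 9.4 summarises the number of inhalation events. No section compares self-report with that ungrouped count. The documents do not say whether one time on the five-group scale is a dosing occasion or a single inhalation, and they give no rule for turning a count into a group.

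**The concern.** The device has no ceiling at 3 a day, but the plan gives it one so that it matches the questionnaire. Above that point the two measures are tied whatever the participant did or said. Part of the error the study wants to describe, under-reporting by people who use a lot of rescue medication, cannot appear in the one analysis that compares reported with recorded use. Nor can heavy users be ranked among themselves.

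The loss would survive better-defined cut-points or a signed comparison of the groups, because two values in the same top group always differ by zero. It is also avoidable on the device side, since the finer information is already held.

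**Working it through.** The plan states no correlation, precision or power figure for this outcome, so there is nothing to reproduce.

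**Permitted range (section 6.1.2).** 24/6 = 4 to 24/4 = 6 occasions a day; at 2 inhalations each, 8 to 12 inhalations a day. The top group therefore covers 3 to 6 occasions. If single inhalations are counted instead, it covers 3 to 12 and starts at 3/2 = 1.5 two-inhalation occasions a day.

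**Which misreporting is hidden.** A participant reporting a fraction f of actual use stays in the top group when actual use is at least 3/f: 6.0, 5.0, 4.29 and 3.75 a day for f = 0.5, 0.6, 0.7 and 0.8.

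- Hidden (actual, reported): (6,3), (5,3), (4,3), (6,4).
- Still visible as different groups: (6,2), (4,2), (3,2), (6,1).

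**How many participants.** The documents give no usage distribution, so this rests on assumptions: lognormal occasions per day with log-SD 0.8, floored at one a week and capped at 6 a day; reports equal to 70% of actual use with log-SD 0.3 noise; 200,000 simulated participants per scenario. The gap between the top two groups is undefined, so two cut-points are shown.

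| Assumed median per day | In top device group, cut at 2.5 | In top device group, cut at 3 | Under-reporters hidden, cut at 2.5 | Under-reporters hidden, cut at 3 |
|---|---|---|---|---|
| 1 | 12% | 8.5% | 32% | 28% |
| 2 | 39% | 31% | 46% | 39% |
| 3 | 59% | 50% | 57% | 47% |

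The last two columns are shares of those in the top device group who under-report by at least 20% (about 67% of that group with the cut at 2.5).

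A second set of assumptions used log-SD 1, medians of 0.7, 1.5 and 3 a day, and a cut at 3. Among users at 3 or more a day who misreport by more than 20%, the hidden share was 36% to 56% when reports averaged 70% of actual use, 17% to 29% at 50%, and 76% to 85% when reports were noisy but unbiased.

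**Effect on rho (first set, median 2, cut at 2.5).**

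- Both sides in five groups: 0.75.
- Self-report grouped, device ungrouped: 0.84.
- Neither grouped: 0.93.

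**How much of that is the ceiling.** Removing only the ceiling on both sides, with the lower groups kept, moves rho from 0.77 to 0.77, 0.75 to 0.81 and 0.72 to 0.83 at medians 1, 2 and 3. At median 2 the ceiling accounts for 0.81 − 0.75 = 0.06 of the total loss of 0.93 − 0.75 = 0.18, or one third; coarse grouping lower down accounts for the rest. Under the second set, splitting the top group into three (3 to under 4, 4 to under 5, 5 or more) changed rho by at most 0.04.

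**The case against.** The strongest reply is that this is a modest loss of resolution in a descriptive pilot of 60 without a power calculation. Much of that stands.

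- A reader might infer that all misreporting by the heaviest users is scored as agreement. The documents do not support this. Anyone who drops below 3 a day changes group and is seen, and in the first set of assumptions 43% to 72% of top-group under-reporters remain visible (100 − 57 to 100 − 28).
- A reader might infer that the coefficient is inflated. Section 9.4 specifies a rank correlation, not an agreement statistic, and grouping lowered rho in every scenario run.
- A reader might infer that the scale fails to cover expected use. Section 6.1.2 describes an as-needed schedule, which bounds use but does not predict it, and entry requires only one puff a week. An open-ended top answer does cover the range; it only lacks detail.
- The ungrouped count is used elsewhere, including in the exploratory analysis of the 7 days around an exacerbation. A four-week average recall could not detect an abrupt rise at any resolution, so that part of the rationale is not harmed here.

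What remains is that the only comparison of reported with recorded use discards device information the study already has.

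**Conclusion.** The point holds in a limited form and is minor. Misreporting that stays at or above 3 a day cannot be seen in secondary outcome 1, and heavy users cannot be ranked, because the device count is cut to the questionnaire's groups. The shared ceiling and the 4 to 6 permitted occasions follow directly from sections 9.4 and 6.1.2.

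The size depends on assumed usage. About 9% to 59% of participants fall in the top group across medians of 1 to 3 a day and the two cut-points, and between about a quarter and just over half of the under-reporters there are hidden when reports average 70% of actual use. The cost to rho is a reduction, and at median 2 a day most of it comes from coarse grouping in general.

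Separately, a rank correlation cannot test the directional hypothesis in section 9.1, with or without a ceiling.

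**What to change.** In section 9.4 and the synopsis:

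1. Keep the planned five-group Spearman coefficient.
2. Add the Spearman coefficient of the self-report group against the ungrouped Digihaler rate per day, taken over the same four-week recall window. State whether the rate counts occasions or inhalations.
3. Tabulate the median and range of the device rate within each answer group, especially the top one.

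This is plan wording plus one coefficient and one table from data already captured. It shows how widely actual use varies among people who give the top answer, but it does not remove the ceiling in the self-report.

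Optionally, a numeric follow-up on puffs per day at the monthly calls would remove that ceiling. It needs a CRF and IRB amendment, gives noisier recall, and would be missing for calls already made, so it should supplement the grouped item rather than replace it.
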